4.5. End of participation

Participation in the study will be terminated once all study procedures including treatment and follow-up sessions are completed or under circumstances warranting participant withdrawal from the study (see section "7. Subject Monitoring"). Participants can also withdraw from the study at any time should they no longer wish to participate. Participants who withdraw from the study will be provided with information regarding alternative treatment options within the community. If participants decide during the pre-treatment study phase that they wish to quit smoking immediately (that is, prior to completing their pre-treatment scan sessions), they will be withdrawn from the study and provided information regarding alternative treatment options within the community. If participants withdraw during the treatment phase of the study, they will be asked if they wish to consent to be contacted at the three follow-up points. They will also be provided with information regarding alternative treatment options within the community should they wish to seek treatment elsewhere. Typically, no data obtained during the course of this study will be shared with the individual participant or their health care providers.

4.6. Relationship to other protocols.

All participants will be asked to participate in protocol 10-DA-N457. Participation in protocol 10-DA-N457 is required for inclusion in the current study. Genotyping and blood draw for genotyping described in the current protocol will carried out under protocol 10-DA-N457. Participants who complete the Motivational Interviewing Arm of the study (see Section 22) may be offered admission to protocol 13-DA-N485.

5. Storage of data and samples

Clinical data will be stored in the Clinical Data Warehouse (CDW) and in clinical research charts or research binders. Research charts or binders will be stored in locked filing cabinet, in a locked room at the NIDA-IRP. Imaging data are stored on a password protected drive on a UNIX server, which is maintained by the NRB. One copy of the consent form is kept in the participant's NIDA-IRP medical chart, the other is kept in a limited access, locked cabinet with other consent forms from the same protocol. Summaries of data analyses (e.g. demographics, clinical laboratory results, consent audit) are stored on a password protected shared NRB data drive. Participant data contained within files on the NRB data drive are identified by ARC number, and not by other personal identifiers such as name.

Plasma samples acquired for measurement of cortisol and ACTH, will be destroyed once valid assays have been obtained.

Principal Investigator: [name].

6. Data Sharing Plan

Unless specified otherwise, data collected in this study may also be combined with data collected across IRB approved protocols, including the NRB Repository Protocol, 06-DA-N802 and the NRB protocol, 10-DAN-457, "Characterization of Phenotypic and Genotypic Regressors to allow for greater power to detect otherwise small effect size analyses untestable with a single data set. Additionally, de-identified data may be shared with properly administered databases and/or with collaborators with whom proper data sharing agreements are in place.

Date: March 2, 2022

7. Additional Considerations

N/A

8. Risks/ discomforts

8.1. Questionnaire and Characterization Measures.

The questions asked may be perceived as embarrassing or may cause anxiety or distress. Nevertheless, such reactions are expected to be temporary and to rapidly dissipate spontaneously.

Risk Minimization. Participants will be advised prior to completing these measures that they may refuse to answer any questions that cause them discomfort. Furthermore, any participant who experiences anxiety or distress as a result of these assessments will be able to speak to a NIDA-IRP mental health professional to discuss this.

8.2. Nicotine Patch Administration.

Adverse events (AEs) related to the nicotine patch include:

- Abdominal Pain
- Chest pain
- Coughing
- Diaphoresis
- Dizziness
- Dry mouth
- Headache

- Palpitations
- Rash
- Restlessness
- Sleepiness
- Temporary mood change
- Minor skin irritation
- Nausea/Vomiting

The most common possible side effects of nicotine patch administration are skin irritation, sleep disturbances, and nausea and vomiting. All effects are temporary and will dissipate spontaneously and quickly (1-2 hrs) after patch removal.

More severe toxic effects of nicotine may include cardiac tachyarrythmias, hypertensive crisis, dizziness, weakness, confusion, and convulsions. The lethal dose of nicotine in adults is from 0.5-1.0 mg/kg or a total single bolus dose of 40-60mg (http://www.cdc.gov/mmwr/preview/mmwrhtml/mm5218a3.htm) (US-EPA. Chemical

Principal Investigator: [name].

profile: Nicotine. US Environmental protection Agency 1987). Nicotine death may likely result from paralysis of respiratory muscles or central respiratory failure. Individuals likely have widely different levels of tolerance to the toxic effects of nicotine based on previous exposure. Nicotine patch doses up to 63mg/d have been shown to be safe and generally well-tolerated by smokers (Zevin et al., 1998; Ebbert et al., 2007). Most reports of nicotine poisonings and deaths are typically the result of contact with nicotine-containing pesticides (Benowitz et al., 1987). Although ingestion of nicotine is common, deaths due to poisoning are extremely rare, due to early vomiting and the short half-life of the drug. In the current protocol, the protracted release of nicotine via the transdermal (24hr) patch should keep nicotine plasma concentrations well within a safe range. If participants show initial signs of nicotine poisoning during the patch-toleration test (i.e., burning throat, nausea, vomiting) they may be excluded from further participation depending on the severity of their symptoms

Date: March 2, 2022

Risk Minimization. In order to minimize risks associated with nicotine, only individuals who meet certain medical history criteria will be recruited into the study. Participants will be clearly instructed on potential side-effects during their orientation visit and will be provided with a phone number to speak with a research team member should they experience any side-effects following patch application. These instructions will be re-iterated to all participants over the phone when they are contacted to commence their abstinence periods. They will be given identical instructions prior to both the placebo and nicotine-patch abstinence periods. During imaging visits, all subjects receiving a nicotine or placebo patch will be monitored for blood pressure, respiratory rate, and pulse rate changes prior to scanning sessions and compared to their admission baseline values. Nicotine or placebo patch administration will be terminated immediately upon participant's request.

8.3. Varenicline administration. (Applicable to treatment-seeking smokers only)

Varenicline is being used in accordance with its FDA-approved labeling in this study. The most frequent AE reported in varenicline treatment groups during Phase II and III trials were nausea, insomnia, abnormal dreams, and headaches (Gonzales et al., 2006; Jorenby et al., 2006; Nides et al., 2006; Oncken et al., 2006). Nausea, the most common AE, was reported by ~30-50% of participants receiving varenicline in comparison to ~10% of those receiving placebo (Glover and Rath, 2007). Reports of nausea are typically described as transient and mild to moderate in severity. Discontinuation rates for varenicline are generally similar to those seen for placebo- and buproprion-groups in these trials (e.g., Nides et al., 2006). Titration of doses has been shown to reduce the overall incidence of nausea to ~16-34% (Oncken et al., 2006). Generally, very few participants (i.e., < 5%) discontinue study medication because of nausea (Oncken et al., 2006). A long-term study assessing the safety and efficacy of varenicline administration concluded that varenicline can be safely administered for up to 52 weeks, the duration of that study (Williams et al., 2007). Based on extant clinical data there appear to be no clinically meaningful pharmacokinetic drug-drug interactions and no evidence for human abuse liability (Glover and Rath, 2007).

Other discomforts that have been reported include vomiting, abdominal pain, gas, indigestion, constipation, reflux, dry mouth, diarrhea, and mouth ulceration. Additional frequent side effects include difficulty sleeping (18%), abnormal dreams and nightmare (13%), headache (15%), feeling fatigued or sleepy (7%), and change in appetite (3%). Additional listed side effects include tinnitus (ringing ear), increased urination, blurred vision, sweating, hot flush, increase or decrease of blood pressure, increased heart rate or palpitation, flu-like symptoms, drug allergy, abnormal liver function test, increase in weight, abnormal electrocardiogram, back and muscle pain, disturbance in attention, dizziness or fainting, feeling restless, anxiety, depression or euphoria, irritability, and agitation. A complete list of the expected AEs and side effects can be found in the drug insert (see attached chantix_pfizer_insert.pdf). In addition, based on Pfizer and FDA's ongoing safety review of post-marketing reports, Pfizer recently updated the varenicline label in the U.S. to include a warning that patients who are attempting to quit smoking with varenicline should be observed for serious neuropsychiatric symptoms, including changes in behavior, agitation, depressed mood, suicidal/violent ideation, and suicidal/violent behavior. Pfizer

Principal Investigator: [name].

also stated that a causal relationship between varenicline and these reported symptoms has not been established. In some reports, however, an association could not be excluded. More specifically, some reports may have been complicated by the symptoms of nicotine withdrawal in patients who stopped smoking, but not all patients with these symptoms had quit smoking. Some patients with pre-existing psychiatric illness experienced a worsening of their conditions. A recent report compared patients with mental illness and patients with no mental illness who were on varenicline treatment for smoking cessation reported that "there was no evidence that varenicline exacerbated mental illness" (Stapleton et al., 2008).

Date: March 2, 2022

A recent case report describes multiple episodes of severe hypoglycemia experienced by a 51 year old Type-I diabetic after the onset of varenicline treatment (Kristensen et al., 2008). The discontinuation of varenicline resolved any further hypoglycemic episodes. Thus, it is possible that diagnosed/undiagnosed diabetics may experience severe hypoglycemic episodes while taking varenicline. In the consent, severe hypoglycemic events will be noted as a potential side effect.

A list of treatment-emergent adverse events reported by patients during all clinical trials involving varenicline indicates that cardiac issues (e.g., arrhythmia, myocardial infarct) occurred infrequently (Pfizer insert). Given that cigarette smoking has a negative impact on the heart and the potential for cardiac side effects, in the consent cardiac disorders are noted as a potential side effect.

Risk Minimization. Only individuals who meet certain medical history criteria will be recruited into the study. Participants with a history of heart problems, diabetes, or abnormal renal functions will not be included in the present study. Doses will be titrated to reduce the severity/incidence of side effects. The daily dose of varenicline may be reduced (on a case-by-case basis) to alleviate side effects such as nausea. We have excluded individuals with current or past major psychiatric illness, and will closely monitor potential psychiatric symptoms, depression, and suicidal ideation as part of the clinical monitoring plan. The monitoring plan (see Section 8 Subject Monitoring) consists of weekly in-person assessments at NIDA-IRP during 12 week treatment visits. Drug administration procedures will be terminated immediately upon participant request. In the event of a severe side effect such as a hypoglycemic event, myocardial infarction/arrhythmia, or increase in suicidal ideation, participants will be advised to immediately discontinue study pill administration. If seeking medical care, participants will be instructed to notify their physician or medical care providers of the fact that they are taking varenicline.

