3.2. Inclusion criteria

All participants must:

- (1) Be between the ages of 18-55. Be right-handed. Assessment tool(s): Edinburgh Handedness Inventory.
- (2) Be in good health. *Justification:* Many illnesses may alter fMRI signals as well as cognitive processes and neural functioning. *Assessment tool(s):* Participants will provide a brief health history during phone screening, and undergo a medical history and physical examination with a qualified IRP clinician.
- (3) Be free of active DSM-IV dependence, or dependence in partial remission, on alcohol or any drug except nicotine. Past active dependence is acceptable provided it is at least five years in the past and total time of active dependence did not exceed 4 years. Those with past dependence on any substance other than alcohol or marijuana may not have any current use (past 6 months) of the substance on which they were dependent. For individuals with past alcohol or marijuana dependence, current use of the previously

Principal Investigator: [name].

dependent substance will be allowed providing they do not meet any current DSM-IV criteria for substance dependence, with the exception of tolerance. *Justification*: Dependence on other substances (drugs or alcohol) may result in unique CNS deficits that could confound results and introduce excessive variance. *Assessment tool(s)*: The computerized SCID and clinical substance abuse/dependence assessment. While recreational/intermittent use of alcohol and/or marijuana will be tolerated in all participant groups, individuals will be excluded if they meet current or recent (within 5 years) DSM-IV diagnostic criteria for dependence on any substances. A positive drug test for marijuana will not be exclusionary as long as participants have not used in the 24hrs preceding the imaging visits. In the event of a positive drug test for marijuana, self-reports of current marijuana use will be used to differentiate intermittent/infrequent from chronic/frequent users. Given a possible link between marijuana use and psychosis (Ben Amar and Potvin, 2007) frequent users, defined as those using twice or more per week within the last month, will be excluded from participation.

Date: March 2, 2022

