- (5) have any current neurological illnesses including, but not limited to, seizure disorders, frequent migraines or on prophylaxis, multiple sclerosis, movement disorders, history of significant head trauma, or CNS tumor. *Justification:* Neurological diseases alter CNS function and, possibly, the neuronal-vascular coupling that forms the basis of the fMRI signal. *Assessment tool(s):* History and physical examination by a qualified IRP clinician, urine drug screening for anticonvulsants not disclosed by history. History of head trauma with loss of consciousness of more than 30 minutes or with post-concussive sequelae lasting

Principal Investigator: [name].

more than two days, regardless of loss of consciousness, will be exclusionary. The MAI who will also retain discretion to exclude based on a history of neurological illness that may compromise data integrity.

Date: March 2, 2022

- (6) Have any current major psychiatric disorders to include, but not limited to, mood, anxiety, psychotic disorders, or substance-induced psychiatric disorders, or any current suicidal ideations or history of suicide attempts or currently under antidepressant or antipsychotic medication treatment. The MAI will reserve the right to exclude on the basis of psychiatric history not explicitly described in this criterion *Justification:* Psychiatric disorders involve the central neural system (CNS) and, therefore, can be expected to alter the fMRI measures being used in this study. A recent FDA communication (2/1/2008) indicates that there may be an association between varenicline and the worsening of current psychiatric illness even if the illness is currently under control. *Assessment tool(s):* Computerized SCID, Beck Depression Inventory, Beck Anxiety Inventory, Adult ADHD Self-Report Scales and clinical interview confirmation by clinician.
- (7) Are cognitively impaired or learning disabled. *Justification*: Cognitive impairment and learning disabilities may be associated with altered brain functioning in regions recruited during laboratory task performance. Cognitive impairment may affect one's ability to give informed consent. *Assessment tool(s)*: History of placement in special-education classes as a consequence of serious learning problems and not solely as a consequence of behavioral problems, assessed during the History and Physical screening assessment.

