(11) are non-English speaking. Justification: To include non-English speakers, we would have to translate the consent and other study documents and hire and train bilingual staff, which would require resources that we do not have and could not justify given the small sample size for each experiment. Additionally, the data integrity of some of the cognitive tasks and standardized questionnaires used in this study would be compromised as they have only been validated in English. Most importantly, ongoing communication regarding safety procedures is necessary when participants are undergoing MRI procedures. The inability to effectively communicate MRI safety procedures in a language other than English could compromise the safety of non-English speaking participants. Assessment tool(s): self-report.

Treatment-seeking smokers will also be excluded if they:

- (12) have moderate to severe renal impairment. *Justification. Given that renal* secretion is varenicline's major route of clearance, kidney impairment may result in higher systemic levels of the drug than intended. Per Pfizer's chantix insert, varenicline pharmacokinetics were *unchanged in subjects* with mild renal impairment in comparison to those with normal renal function, whereas individuals with moderate and severe impairment presented with varenicline levels 1.5 and 2.1-fold higher, respectively. *Assessment tool(s): Estimated* glomerular filtration rate. Renal insufficiency with estimated creatinine clearance < 60 ml/min calculated by the Cockcroft-Gault equation will be excluded.
- (13) are diabetic. *Justification*. A recent case report describes multiple episodes of severe hypoglycemia experienced by a 51 year old Type-I diabetic after beginning varenicline treatment (Kristensen et al., 2008). The discontinuation of varenicline resolved any further hypoglycemic episodes. The safety of varenicline has not been investigated in patients with diabetes. *Assessment tool(s)*: Casual plasma glucose testing. Individuals with glucose levels above 200 mg/dl may be further evaluated for diabetes using a fasting glucose test or be excluded.

4. Study Design and Methods:

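### Section 8.3 states that past major psychiatric illness is excluded before varenicline, but criterion 6 and the Main Study checklists mandate exclusion only for current disorders

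*Combined protocol and SAP*

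**What the plan says.** Section 8.3, whose title marks it "Applicable to treatment-seeking smokers only", ends with a risk-minimization paragraph. Among the measures listed is that "We have excluded individuals with current or past major psychiatric illness". The same sentence adds close monitoring of psychiatric symptoms, depression and suicidal ideation.

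The operative rule is exclusion criterion 6 in Section 3.3. It removes people who "Have any current major psychiatric disorders to include, but not limited to, mood, anxiety, psychotic disorders, or substance-induced psychiatric disorders", and adds "any current suicidal ideations or history of suicide attempts or currently under antidepressant or antipsychotic medication treatment". It then says that "The MAI will reserve the right to exclude on the basis of psychiatric history not explicitly described in this criterion".

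Both Main Study checklists in Appendix 1 (474-treatment and 474-Nontreatment, medical exclusion 7) carry the same rule, with the word current. Section 3.3 then opens a further list with "Treatment-seeking smokers will also be excluded if they". That list has two items: renal impairment (12) and diabetes (13).

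**The concern.** Section 8.3 reports a completed safeguard to anyone weighing the risk of the drug. The text around it shows why the safeguard is offered. Section 8.3 describes the label warning on neuropsychiatric symptoms and notes that some patients with pre-existing psychiatric illness got worse. The justification for criterion 6 cites a possible worsening on varenicline even in illness that is under control. If the screening rule does not require what the risk section says has been done, the risk section overstates the protection in place, and people it calls excluded can reach the drug. Enrolment is decided by the criteria and checklists, not by the risk section.

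**Working it through.** No rate, sample size or error level enters this point, so there is nothing to calculate. The check is a comparison of texts.

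| Element | Section 8.3 | Criterion 6 and checklist item 7 |
|---|---|---|
| Current major psychiatric disorder | Excluded | Excluded |
| Past, resolved major psychiatric disorder | Excluded | Not mandatory; MAI may exclude |
| Current suicidal ideation | To be monitored; no exclusion stated | Excluded |
| History of suicide attempts | Not mentioned separately | Excluded |
| Current antidepressant or antipsychotic treatment | Not mentioned separately | Excluded |

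1. *Scope.* Section 8.3 concerns treatment-seeking smokers, the group offered varenicline. The relevant rules are the criteria for all Main Study participants, the additional treatment-seeker exclusions and the 474-treatment checklist. The tDCS criteria are worded differently but do not bear on this.

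2. *Is past disorder excluded anywhere else?* The additional treatment-seeker exclusions cover only kidney function and diabetes. Diabetes and renal function also appear in the Section 8.3 paragraph, and each has a matching exclusion. Past psychiatric illness has none. Substance dependence has its own rule, inclusion criterion 3 in Section 3.2, where "Past active dependence is acceptable provided it is at least five years in the past", with further conditions. So that rule does not supply a general bar on past disorder either.

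3. *Test case.* Take a treatment-seeking smoker with a past mood, anxiety or psychotic disorder, no current disorder, no current suicidal ideation, no suicide attempt, and no current antidepressant or antipsychotic treatment. Each mandatory element of criterion 6 is answered no, and so is checklist item 7. Subject to the other criteria, this person is eligible unless the MAI uses the reserved right to exclude. Section 8.3 counts the same person as excluded.

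4. *The rest of the safeguard.* Monitoring is specified. Appendix 7 sets a weekly varenicline toleration interview, in person or by telephone, continuing for two weeks after the last dose. Section 9.1 refers any endorsed item to the MAI or a covering clinician. Only the past-illness element lacks a rule.

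**The case against.** The best defence is that Section 8.3 is a summary and that Section 3.3 and Appendix 1, which agree with each other, govern screening. Staff are therefore not applying conflicting rules. The MAI may exclude on psychiatric history and, under criterion 9, reviews all screening data. The participant also meets the MAI or a designated physician about the medication before treatment. This stands as far as it goes: the defect is a misdescribed safeguard. But an optional right to exclude does not support a flat statement that a group has been excluded, and it lets entry vary from case to case.

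A reader might infer three stronger things that the documents do not support:

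- *That anyone with past illness will receive the drug.* The MAI's discretion makes this a possibility, not a certainty.
- *That the safeguard is absent.* Current disorders, current suicidal ideation, past suicide attempts and current antidepressant or antipsychotic treatment are all excluded, and the monitoring is laid out in detail.
- *That the anhedonia and negative-affect results are compromised.* The deprived versus non-deprived comparison in Section 11.2 is within-subject, so a stable history is the same in both conditions. The documents give nothing from which an effect on these outcomes could be established.

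Nor is history left ungathered. Section 4.3 already includes a detailed medical history, a SCID-based screen and the Beck depression and anxiety inventories, although it does not say whether the screen yields lifetime diagnoses.

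**Conclusion.** The inconsistency is real and lies in current text. Followed as written, the screening rule can admit to varenicline people whom Section 8.3 says are excluded. The number cannot be stated. The affected group is some part of the 120 planned treatment-seeking enrollees, and the documents give neither the share with past disorder nor how often the MAI would exclude. The conclusion rests on reading criterion 6 as written, with current governing the listed disorders and the MAI's right being optional. It does not show harm, and it does not settle which text reflects the intended rule. A correction should be made because a safety statement does not match the criteria meant to deliver it.

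**What to change.** Reconcile the Section 8.3 risk-minimization paragraph with criterion 6 in Section 3.3 and item 7 of the two Main Study checklists in Appendix 1, so that a single rule on past psychiatric illness is stated and screened for. Which rule to adopt is for the investigators to decide on clinical grounds, and none is proposed here. If Section 8.3 is changed to match the criteria, the cost is a sentence. If the criteria are changed to match Section 8.3, the checklists change too and some candidates will be lost. No new data collection is needed; psychiatric history already gathered at screening may be described when the sample is reported.
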